IDMC = Independent Data Monitoring Committee.

¹ IDMC to review safety data through Week 1 for 12 subjects in group a before enrollment will begin in b and c.

² IDMC to review safety data for all subjects within each age group and initial immunogenicity data from Part 1, to make recommendations on dose selection for randomized, placebo-controlled phase, before enrollment begins in Part 2.

Cohorts 1 and 2 (naïve and prior vaccinated subjects, respectively) will enroll in parallel, and the IDMC may review safety data for the two Cohorts separately if the enrollment rates between the two groups vary.

After signing an informed consent, participants will undergo screening assessments to determine study eligibility over a 30-day Screening Period.

On Day 1, eligible participants will be enrolled sequentially to receive their 1st oral vaccination according to their assigned treatment group as specified in Table 1.

During the Active Period, participants will record daily symptoms of reactogenicity for 1 week post each vaccination, administered on Day 1 and Week 4, using a Solicited Symptom Diary. They will return to the site at 1 and 4 weeks following each vaccination, as specified in the SoA, to have safety assessments and samples collected for evaluation of immunogenicity. Post completion of the Week 1 visit by all subjects in a specified cohort, as detailed in

Table 1, the Independent Data Monitoring Committee (IDMC) will review Day 1 to Week 1 safety data and make recommendations as to whether to proceed to the next cohort(s). Upon completion of active portion of Part 1, the IDMC will review safety and preliminary immunogenicity data from all cohorts and make recommendations to the Sponsor on the VXA-CoV2-1.1-S dose level to evaluate in Part 2. A summary of safety and immunogenicity data with the intended dose for Part 2 will be submitted to FDA for review and concurrence prior to initiation of enrollment in Part 2.

At the Week 4 visit participants will have safety assessments to evaluate suitability to receive the second vaccination as outlined in Section 3.2.2. Participants with any of the following conditions will not be eligible to receive a second vaccine dose:

- Positive pregnancy test at Day 29 (female participants),
- Occurrence of any possibly, probably or definitely treatment-related Grade 3 or 4 AE or SAE following the initial vaccination

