Any participant reporting COVID-19 like illness or exposure to COVID-19 will be asked to return to the site for an unscheduled visit to test for SARS-CoV-2 infection. Participants with confirmed SARS-CoV-2 infection, at any time during the study period, will be asked to provide a nasal swab every two days after their confirmatory COVID-19 test, until they are negative, to monitor for duration of infection. They will also be monitored for clinical disease severity (Section 7.1.1, Table 6), and outcome, including potential VAED. The participant will be counseled to notify their Primary Care Physician of their positive SARS-CoV-2 status and seek medical care should they become symptomatic.

Participants will be followed via site visits and monthly phone calls in order to monitor for COVID-19 (symptoms or exposure) starting from 7 days following their second vaccination in the Active Period. The study Efficacy Period, as described in Duration of Study Participation in Table 2, will last until the last participant randomized has completed their Month 7 visit (6 months post last study drug administration), after which the study database will be cleaned and locked, and the primary efficacy analyses performed. At this time the treatment assignments will be unblinded and Part 2 participants in the placebo group will have the opportunity to receive vaccination(s) against COVID-19 as detailed in Section 5.9.

An interim analysis for efficacy may also be performed if 18 cases of confirmed COVID-19 are reported prior to the planned efficacy analysis at completion of Month 7 visits by all participants.

The IDMC will provide safety oversight throughout the duration of the study. If the protocol halting rules are met at any time during the study (refer to Section 6.1.1 for Part 1 and Section 6.1.2 for Part 2), enrollment and dosing will be suspended pending a full IDMC review (Section 8.5.2). The Sponsor's Medical Monitor(s) (or designees) will perform safety oversight (Section 8.5.1).

Treatment Group and Number of Participants

Part 1 – Open-Label Lead-in (N = ~ 72 Participants)

This phase will include healthy male and female adult volunteers 18 to 75 years old, inclusive, in the following cohorts:

- **Cohort 1-** Healthy adults who are naïve (no prior vaccinations against COVID-19 and no history of COVID-19) and are at low risk of developing severe COVID-19 upon potential infection with SARS-CoV-2

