Any participant reporting COVID-19 like illness or exposure to COVID-19 will be asked to return to the site for an unscheduled visit to test for SARS-CoV-2 infection. Participants with confirmed SARS-CoV-2 infection, at any time during the study period, will be asked to provide a nasal swab every two days after their confirmatory COVID-19 test, until they are negative, to monitor for duration of infection. They will also be monitored for clinical disease severity (Section 7.1.1, Table 6), and outcome, including the potential for VAED. The participant will be counseled to notify their Primary Care Physician of their positive SARS-CoV-2 status and seek medical care should they become symptomatic.

Participants will be followed via site visits and monthly phone calls in order to monitor for COVID-19 (symptoms or exposure) starting from 7 days following their second vaccination in the Active Period. The study Efficacy Period will last until the last participant randomized has completed their Month 7 visit (6 months post last study drug administration), after which the study database will be cleaned and locked, and the primary efficacy analyses performed. At this time the treatment assignments will be unblinded and Part 2 participants in the placebo group will have the opportunity to receive vaccination(s) against COVID-19 as detailed in Section 5.9.

An interim analysis for efficacy may also be performed if 18 cases of confirmed COVID-19 are reported prior to the planned efficacy analysis at completion of Month 7 visits by all participants.

The IDMC will provide safety oversight throughout the duration of the study. If the protocol halting rules are met at any time during the study (refer to Section 6.1.1 for Part 1 and Section 6.1.2 for Part 2), enrollment and dosing will be suspended pending a full IDMC review (Section 8.5.2). The Sponsor's Medical Monitor(s) (or designees) will perform safety oversight (Section 8.5.1).

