6. DISCONTINUATION OF STUDY DRUG AND SUBJECT WITHDRAWAL FROM STUDY

6.1. Study Halting Rules

The study will be halted (no new enrollments and no further study vaccinations) pending an IDMC safety review if any of the below rules are met prior to the start of randomization in Part 2, or the end of the Active Period (4 weeks after the last study drug) in Part 1, whichever is later.

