6.2. Discontinuation of Study Drug

In some instances, it may be necessary for a participant to permanently discontinue study drug (that is, not receive the second vaccination). Please also refer to halting rules described in Section 6.1.

Permanent discontinuation of study drug does not mean withdrawal from the study, and the participant will be encouraged to remain in the study and continue to complete all study visits. At the time of treatment completion or study drug discontinuation, the Early Termination (ET) visit should be completed as shown in the SoA (Section 1.2). Participants should continue to be followed for safety, immunogenicity and efficacy even if they discontinue study drug prematurely unless they withdraw consent.

Participants may discontinue or be discontinued from study drug at any time. A participant may discontinue study drug for reasons including but not limited to:

- Adverse event
- Death
- Lost to follow-up
- Physician decision
- Pregnancy
- Protocol deviation
- Study terminated by Sponsor
- Withdrawal by participant* (*only for discontinuing study drug, but will remain in study)

The reason for participant discontinuation from study drug will be recorded in the eCRF.

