8.5. Safety Oversight

8.5.1. Internal Sponsor Review

Safety data will be monitored on an ongoing basis by the Investigator (or medically qualified designee) and the Sponsor's Medical Monitor (or designee) in order to promptly identify and flag any event that potentially contributes to a halting rule (Section 6.1).

A Sponsor's Medical Monitor (or designee) will perform the oversight of safety for this study. Additional local medical monitors may also be employed to aid with safety oversight locally. The lead Medical Monitor will be a physician experienced in the conduct of research clinical studies whose primary responsibility will be to monitor participant safety. The Medical Monitor will be responsible for reviewing the cumulative safety data, including a review of safety laboratory test results and adverse event reporting. The Medical Monitor will be familiar with study-specific data as well as relevant background information about the disease, investigational drug, and target population under study. The Medical Monitor(s) will be empowered to request an IDMC safety review which can suspend the study, recommend amendments to the protocol, and/or to request further information.

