8.5.2. Independent Data Monitoring Committee (IDMC)

An IDMC will be assigned by the Sponsor prior to the beginning of the study and will provide ongoing oversight of the study.

The IDMC will provide study oversight throughout the duration of the study period (Day 1 through EOS). The IDMC will perform a review of safety data of all participants in Part 1. Enrollment and dosing in Part 2 will only commence following the IDMC's recommendation to proceed. A summary of safety and immunogenicity data with the intended dose for Part 2 will also be submitted to FDA for review and concurrence prior to initiation of enrollment in Part 2.

In Part 2, unblinded data will be provided to the IDMC to ensure halting rules are applied based on observations of events in the vaccine treatment groups, regardless of dose level.

Additionally, *ad hoc* meetings will be convened if any predefined halting rules (see Section 6.1) are met, any serious vaccine related events or trends are observed, or the IDMC has concerns of potential vaccine enhanced disease (following the occurrence of a COVID-19, as defined in Section 7.1.1).

Further details regarding data safety monitoring guidelines will be included in the IDMC Charter, which is the governing document that supersedes this section of the protocol.

_

Vaxart, Inc.

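### Section 6.1 states one halting period for both rule lists that ends around the start of Part 2, so the Part 2 rules have no correct period where the Medical Monitor and the IDMC are told to look

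*Combined protocol and SAP*

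**What the plan says.** The lead-in to Section 6.1 stops new enrolment and further vaccination, until the IDMC has looked at the safety data, "if any of the below rules are met prior to the start of randomization in Part 2, or the end of the Active Period". It then defines that Active Period as ending 4 weeks after the last Part 1 dose and takes the later of the two dates. Both lists sit below this sentence: 6.1.1 for Part 1 and 6.1.2 for Part 2. Section 6.1.2 gives four rules, two of them with a five-participant threshold, but no start or stop date.

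Elsewhere the period is different. Section 4.2.2, in the Part 2 design, opens its halting sentence with "If the protocol halting rules are met at any time during the study". The synopsis gives the same sentence and the consequence: "Section 6.1.2 for Part 2), enrollment and dosing will be suspended pending a full IDMC review". Section 3.2.2 and the synopsis text for Part 1 say the same.

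Section 8.5.2 adds "In Part 2, unblinded data will be provided to the IDMC to ensure halting rules are applied".

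Three places send the reader to Section 6.1 for the rules:
- Section 8.5.1, where safety data are monitored so as to "promptly identify and flag any event that potentially contributes to a halting rule (Section 6.1".
- Section 8.5.2, where ad hoc "meetings will be convened if any predefined halting rules (see Section 6.1) are met".
- Section 6.2, a bare cross-reference: "Please also refer to halting rules described in Section 6.1".

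**The concern.** The lead-in's period is defined by the start of Part 2 and the end of Part 1. That cannot suit rules meant to govern Part 2 dosing, yet its wording reaches both lists. A person flagging events against Section 6.1, as Section 8.5.1 directs, finds Part 2 thresholds under a period that has closed or is about to close. A person working from Section 4.2.2 finds the same thresholds in force for the whole study. No current text says which prevails.

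The mismatch also touches Part 1. Those participants are followed to Month 13. If one has a vaccine-related SAE after the Section 6.1 period has ended, Section 3.2.2 calls for suspension and Section 6.1 does not. Whether dosing stops should not depend on which section is open.

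**Working it through.** The plan gives no figure to reproduce. The check has two steps: how much of Part 2 the Section 6.1 period covers if read alone, and whether that agrees with the other sections.

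**Inputs**
- Dose 2 is at Day 29, with a window of +7 days, so Day 36 at the latest (Tables 3 and 4).
- The Part 1 Active Period ends 4 weeks after the last dose (Section 6.1): Day 29 + 28 = Day 57, or Day 36 + 28 = Day 64.
- The Section 6.1 period ends at the later of the first Part 2 randomization and that date for the last Part 1 participant.
- The dose review that precedes Part 2 is timed in three ways. Synopsis: "Upon completion of active portion of Part 1, the IDMC will review safety and preliminary immunogenicity data from all cohorts". Section 3.2.1: once Part 1 enrolment is complete. Section 3.2.3: dose selection rests on Day 8 immunogenicity data.
- FDA concurrence is also needed before Part 2 enrolment (synopsis, Sections 3.2.1 and 8.5.2).

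**Coverage of Part 2 under the literal period**

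| Timing of the dose review | Latest point at which the period closes | Part 2 time covered |
|---|---|---|
| After the Part 1 active portion (synopsis) | First Part 2 randomization | 0 days |
| At the last Part 1 participant's Day 1, no review time (Section 3.2.1, upper bound) | Day 57, or Day 64 with the +7-day window | 57 − 1 = 56 days (8 weeks), or 64 − 1 = 63 days (9 weeks) |
| At the last Part 1 participant's Day 8, no review time (Section 3.2.3) | Day 57, or Day 64 | 57 − 8 = 49 days (7 weeks), or 64 − 8 = 56 days (8 weeks) |

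The second and third rows are ceilings. IDMC and FDA review time comes off both, and the documents do not say how long either takes.

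**Comparison of the texts**

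| Place | Period for the Part 2 rules |
|---|---|
| Section 6.1 lead-in | Ends at the later of Part 2 start and Part 1 Active Period end |
| Section 6.1.2 | None stated |
| Synopsis; Sections 3.2.2 and 4.2.2 | Throughout the study, naming 6.1.2 for Part 2 |
| Section 8.5.2 | No dates, but unblinded Part 2 data go to the IDMC so that the rules are applied |

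The first row cannot be reconciled with the third and fourth under any of the three timings. All of these are current text.

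**The case against.** The best reply is that Part 2 is already covered. The synopsis and Section 4.2.2 contain a mandatory suspension, tied by number to Section 6.1.2 and running for the whole study. Section 8.5.2 gives the IDMC unblinded Part 2 data, and Section 8.5.1 lets the Medical Monitor request an IDMC review that can suspend the study. The literal reading would also make a list headed for Part 2 almost empty, so a sensible reader would take the lead-in as Part 1 wording.

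Most of this stands. A reader might infer that all 1,600 planned Part 2 doses (800 participants × 2) would be given with no halting rule in force. The documents do not support that: the lead-in does not say that halting is confined to its period, and the other sections require suspension independently. Zero days of coverage describes Section 6.1 read alone, not unprotected dosing. A reader might also want the share of Part 2 doses falling inside the period. That needs an accrual rate and review times, which the documents do not give, and it would still not measure unprotected doses.

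The reply does not remove the inconsistency. If the lead-in was meant for Part 1 only, it does not say so, and Section 6.1 would then give Part 2 no period at all, which calls for the same correction. Nor does the IDMC Charter settle it: Section 8.5.2 says the Charter overrides that section, not Section 6.1.

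**Conclusion.** The Section 6.1 lead-in is wrong as written for the Part 2 rules. This is an internal inconsistency in an operative safety rule, not a design choice. Read alone, the section covers no Part 2 dosing on the synopsis timing, and at most about 8 to 9 weeks, less review time, on the Section 3.2.1 timing. The upper figure assumes that Part 2 opens on the last Part 1 participant's Day 1, with 9 weeks requiring full use of the dose-2 window. Since review and FDA concurrence must come first, that ceiling would not be reached.

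The intended rule is clear from the synopsis and Section 4.2.2, and Part 2 has halting protection through them. What remains is that the Medical Monitor and the IDMC are directed to the one section whose stated period is wrong. It should be corrected before Part 2 opens.

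**What to change.** Delete the period from the Section 6.1 lead-in. In its place, state that the 6.1.1 rules apply to Part 1 participants and the 6.1.2 rules to Part 2 participants at any point in the study, and that a halt suspends whatever enrolment and dosing remain, pending IDMC review. This brings Section 6.1 into line with the synopsis and Sections 3.2.2 and 4.2.2. It also avoids choosing a separate end date: once the last dose has been given there is nothing left to suspend.

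The cost is amendment wording only. Thresholds, visits, sample size and analyses do not change.

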3.2.1. Part 1: Enrollment and Initial Vaccination

On Day 1, eligible participants will be enrolled sequentially to receive their 1st oral vaccination according to their assigned treatment group as specified in Table 1.

Population	Cohort	VXA-CoV2-1.1-S Dose Levels*	Age (years)	No of Doses	No. of Participants
Naive	1a	Low Dose: $1x10^{10}$ I.U. $\pm 0.5 \log$	18 - 55	2	12
Prior vaccinated	2a	Low Dose: $1x10^{10}$ I.U. $\pm 0.5 \log$	18 - 55	2	12
IDMC Data Review ¹					
Naive	1b	High Dose: 1x10 ¹¹ I.U. ±0.5 log	18 - 55	2	12
Naive	1c	Low Dose: $1x10^{10}$ I.U. $\pm 0.5 \log$	56 - 75	2	12
Prior vaccinated	2b	High Dose: 1×10^{11} I.U. $\pm 0.5 \log$	18 - 55	2	12
Prior vaccinated	2c	Low Dose: $1x10^{10}$ I.U. $\pm 0.5 \log$	56 - 75	2	12
	IDMC Data Review ²				

* Multiple tablets may be administered to deliver the full intended dose.

[†] Doses will be administered on Day 1 and Week 4.

¹ IDMC to review safety data through Week 1 for 12 subjects in a before enrollment will begin in b or c.

² IDMC to review safety data for all subjects within each age group and initial immunogenicity data from Part 1 to make recommendations to Sponsor on dose selection for randomized, placebo-controlled phase, before enrollment begins in Part 2

Cohorts 1 and 2 (naïve and prior vaccinated subjects, respectively) will enroll in parallel. The IDMC may review safety data for the subgroups within each of these two cohorts separately if the enrollment rates between the two cohorts vary.

During the Active Period, participants will record daily symptoms of reactogenicity for 1 week post each vaccination, administered on Day 1 and Week 4, using a Solicited Symptom Diary. They will return to the site at 1 and 4 weeks following each vaccination, as specified in the SoA, to have safety assessments and samples collected for evaluation of immunogenicity. Post completion of the Week 1 visit by all subjects in a specified cohort, as detailed in

Table 1, the IDMC will review Day 1 to Week 1 safety data and make recommendations as to whether to proceed to the next cohort(s). Upon completion of enrollment in Part 1, the IDMC will review safety and preliminary immunogenicity data from all cohorts and make recommendations to the Sponsor on the VXA-CoV2-1.1-S dose level to evaluate in Part 2. A summary of Part 1 safety and immunogenicity data with the intended dose for Part 2 will be submitted to FDA for review and concurrence prior to initiation of enrollment in Part 2.

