3.2.2. Part 1: Eligibility for Second Vaccination

At the Week 4 visit participants will have safety assessments to evaluate suitability to receive the second vaccination including physical exam, vital signs, pregnancy test (female participants), SARS-CoV-2 rapid molecular test, and assessment of adverse events and new concomitant medication usage. Participants meeting any of the following exclusion criteria will not be eligible to receive their second vaccine administration:

Exclusion Criteria for Second Vaccine Dose:

• Positive pregnancy test at Day 29 (female participants),

Version 5.0

- Occurrence of any possibly, probably or definitely treatment-related Grade 3 or 4 AE or SAE following the initial vaccination
- Occurrence of any Grade 3 or 4 AE or SAE following the initial vaccination without plausible alternative explanation
- Presence of acute illness or significant new medical condition including positive SARS-COV-2 rapid molecular test prior to dosing

Participants deemed ineligible due to presence of acute illness or new medical condition may be re-assessed during the visit window (+7 days), and if the condition resolves, may receive their second vaccination within 1 week of their scheduled Week 4 Visit. In such situations the Principal Investigator must contact the study Medical Monitor and gain consensus on the decision to continue participant with study vaccinations prior to administration of the second dose.

Upon completion of the study Active Period (Week 8 Visit) participants will enter the Safety Follow-up Period and be monitored for SAEs, MAAEs and for exposure to and/or symptomatic COVID-19, including the potential for VAED, through the Month 13/End of Study (EOS). In addition, these participants will be evaluated for immunogenicity as specified in the SoA (Table 3). During the Safety Follow-up Period participants will return to the site at Months 7 and 13 for safety monitoring and collection of samples for evaluation of immunogenicity; they will also be contacted by phone monthly between site visits to query for safety and exposure to and/or symptomatic COVID-19.

Any participant who discontinues study drug early (does not receive the second dose) will enter the Safety Follow-up Period a month earlier at Week 4 and will be monitored for safety and exposure to and/or symptomatic COVID-19 as described above, and complete immunogenicity assessments through EOS per the SoA (Table 3).

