3.2.3. Part 1 Scientific Rationale for Study Design

Part 1 is an open-label, lead-in, dose and age escalation lead-in phase to allow assessing the following parameters in subjects that are naïve to prior vaccination and COVID-19 and those who have received two prior vaccinations against SARS-CoV-2 with an EUA or FDA approved mRNA vaccine:

- Collection of additional safety data in young adults. Though doses as high as two times $1x10^{11}$ IU \pm 0.5 log have been tested with other oral vaccines using the VAASTTM platform, in the Phase 1 study with VXA-CoV2-1 (S and N protein construct), the highest dose tested was $5x10^{10}$ IU \pm 0.5 log due to limited drug product availability. Safety of VXA-CoV2-1.1-S will be evaluated at two dose levels in Part 1 to allow optimal dose selection for the larger, placebo-controlled phase in Part 2; doses to be tested will include $1x10^{10}$ IU \pm 0.5 log (low dose) and $1x10^{11}$ IU \pm 0.5 log (high dose).
- Collection of safety data in older healthy adults with repeat dose administration at the lower dose level . Safety data collected in Part 1 will inform inclusion of this population in Part 2.
- Collection of preliminary data on the immunogenicity of VXA-CoV2-1.1-S vaccine at 2 potentially clinically active doses, 1×10^{10} IU \pm 0.5 log (low dose) and 1×10^{11} IU \pm 0.5 log (high dose). Based on early (Day 8) immunogenicity data from Part 1, the dose level for Part 2 will be selected.

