- 7. Temperature ≥38.0°C (100.4°F) within 24 hours prior to the planned study vaccination (assessment may be repeated during screening period).
- 8. Positive HIV, Hepatitis B surface antigen (HBsAg) or HCV tests at the screening visit.
- 9. History of gastrointestinal bleeding (e.g. melena or hematochezia)

Prior/Concurrent Therapy

Note: The Active Period is defined as the time period from Day 1 through Week 8, or 4 weeks post last vaccination.

- 10. Receipt of a licensed influenza vaccine within 14 days prior to baseline vaccination or another licensed vaccine within 28 days prior to baseline vaccination, or planned administration during the study active period.
- 11. Use of antiviral medications, including anti-retrovirals within 1 week before vaccination or planned use during the active study period.
- 12. Use of antibiotics, proton pump inhibitors, H2 blockers or antacids within 1 week before vaccination or planned use during the active study period.
- 13. Use of medications known to affect the immune function (e.g., systemic corticosteroids and others) within 14 days before vaccination or planned use during the active study period.
- 14. Daily use of nonsteroidal anti-inflammatory drugs, sulfonylureas, and angiotensin II blockers within 1 week before vaccination or planned use during the active study period.
- 15. Positive urine drug screen for drugs of abuse at screening (except for previous marijuana use); concurrent or planned use of marijuana during the active study period.
- 16. Administration of any investigational vaccine, drug or device within 8 weeks preceding vaccination, or planned use within the duration of the study.

Other Exclusions

- 17. Donation or use of blood or blood products within 4 weeks prior to vaccination or planned donation during the study period.
- 18. Any significant hospitalization within the last year which in the opinion of the Investigator or Sponsor could interfere with study participation.
- 19. History of drug, alcohol or chemical abuse within 1 year of screening.
- 20. History of hypersensitivity or allergic reaction to any component of the investigational vaccine, including but not limited to fish gelatin.
- 21. Any of the following history or conditions that may lead to higher risk of clotting events and/or thrombocytopenia:
 - a. Family or personal history of bleeding or thrombosis
 - b. History of heparin-related thrombotic events, and/or receiving heparin treatments

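### Section 6.1 ends the window for all halting rules at or near the start of Part 2, which contradicts the sections that apply the Part 2 rules throughout Part 2

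*Combined protocol and SAP*

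**What the plan says.** Section 6.1 opens with one sentence that governs both lists of rules, 6.1.1 for Part 1 and 6.1.2 for Part 2. New enrollment and further vaccination stop, until the IDMC has looked at the safety data, "if any of the below rules are met prior to the start of randomization in Part 2, or the end of the Active Period" of Part 1. The sentence ends by choosing the later of those two dates. No other window is given for 6.1.2.

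The synopsis (Part 1 and Part 2 design), Section 3.2.2 and Section 4.2.2 all say something different: "If the protocol halting rules are met at any time during the study", with 6.1.2 cited for Part 2, enrollment and dosing are suspended until a full IDMC review. Section 8.5.2 gives the IDMC unblinded data in Part 2 so that the halting rules are applied to events in vaccine recipients.

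The order of the two parts is described in more than one way:
- Synopsis: "Upon completion of active portion of Part 1, the IDMC will review safety and preliminary immunogenicity data from all cohorts". FDA concurrence comes next, then Part 2 enrollment.
- Section 8.5.2: "Enrollment and dosing in Part 2 will only commence following" a favourable IDMC recommendation.
- Section 3.2.1: "Upon completion of enrollment in Part 1, the IDMC will review safety and preliminary immunogenicity data from all cohorts".
- Section 3.2.3: "Based on early (Day 8) immunogenicity data from Part 1, the dose level for Part 2 will be selected".

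**The concern.** The Part 2 rules have their own thresholds: five participants with the same or a similar Grade 3 or higher event, against two in Part 1. They can only have been written to operate once Part 2 dosing has begun. Yet the sentence that switches them on stops applying at about the moment Part 2 begins.

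Part 2 plans 400 vaccine recipients, against about 72 in all of Part 1. Section 6.1 is also the place others are sent to. The duty in 8.5.1 to flag contributing events, and the ad hoc meeting trigger in 8.5.2, both cite it. Suppose a vaccine-related SAE occurs in Part 2. Someone who follows those references would find a window that has already closed, while 4.2.2 says dosing must stop. A halting rule should not need interpretation on the day it is met.

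**Working it through.** The plan states no figure here. The check is a comparison of texts and a timeline.

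**1. Close of the window.** Let R be the first Part 2 randomization and A the end of the Part 1 Active Period. Section 6.1 closes the window at max(R, A). No Part 2 event can precede R, so the Part 2 time covered is max(0, A − R).

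**2. Synopsis sequence.** The IDMC review follows the active portion of Part 1, and FDA concurrence follows the review. So R falls after A, and A − R is negative. Cover is 0 days. Planned Part 2 doses are 800 × 2 = 1,600, and 0 of them fall inside the window.

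**3. Earlier review (3.2.1 and 3.2.3).** Let T be Day 1 of the last Part 1 participant, and r the combined IDMC and FDA review time.
- The second dose is at T + 28. A participant with a resolved acute illness "may receive their second vaccination within 1 week of their scheduled Week 4 Visit", which gives T + 35.
- "The Active Period is defined as the time period from Day 1 through Week 8, or 4 weeks post last vaccination". So A = T + 28 + 28 = T + 56, or T + 35 + 28 = T + 63. If the Week 8 visit takes its full 2-day allowance as well, A = T + 65.
- Section 3.2.1, review once enrollment is complete: R is no earlier than T + r. Overlap is at most 56 − r to 63 − r days (65 − r with the visit allowance).
- Section 3.2.3, Day 8 data: these exist for the last participant at T + 7, so R is no earlier than T + 7 + r. Overlap is at most 49 − r to 56 − r days.

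The widest bounds are 56/7 = 8 weeks to 63/7 = 9 weeks (65/7 = 9.3 with the visit allowance), all less r. The documents do not give r. The assumed values below use the case where the last second dose is 7 days late:

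| Review time r, days (assumed) | 0 | 14 | 28 | 42 | 56 |
|---|---|---|---|---|---|
| Overlap at most, 3.2.1 (63 − r) | 63 | 49 | 35 | 21 | 7 |
| Overlap at most, 3.2.3 (56 − r) | 56 | 42 | 28 | 14 | 0 |

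Part 2 second doses begin 28 days after the first randomization. On the Day 8 reading, none is covered once r reaches 28 days.

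**4. Share of doses, for illustration only.** Suppose the 800 enroll evenly over E days and the overlap is d days, with d no greater than E. Covered doses are 800·d/E first doses plus 800·max(0, d − 28)/E second doses. E is not in the documents either.
- d = 56: E = 60 gives 747 + 373 = 1,120 of 1,600 (70%); E = 90 gives 47%; E = 180 gives 23%.
- d = 28: E = 60 gives 373 of 1,600 (23%); E = 90 gives 16%; E = 180 gives 8%.

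**5. The conflict.** The synopsis, 3.2.2 and 4.2.2 set no closing date for the rules. Section 6.1 closes them at max(R, A). For an event in Part 2 after that date, the two instructions differ on whether enrollment and dosing must stop.

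**The case against.** The strongest reply is that protection in Part 2 is already mandatory. Section 4.2.2 is Part 2 text, and it says that enrollment and dosing will be suspended if the 6.1.2 rules are met at any point. The synopsis and 3.2.2 repeat it. Section 8.5.2 has the IDMC apply the halting rules in Part 2 and convene ad hoc if one is met. A reader might infer from 6.1 that stopping in Part 2 rests on discretion alone. The documents do not support that: one sentence conflicts with several mandatory ones. This part of the reply stands, and it limits the consequence.

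It can also be said that the sentence was meant only for Part 1. It names the Part 1 Active Period, gives no end date for Part 2, and makes good sense as the closing date for the strict Part 1 rules, placed one heading too high. That is probably how it arose. But the sentence does not confine itself to Part 1, and if it did, 6.1 would contain no window or halt instruction for 6.1.2 at all. Either way the text needs correcting.

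The IDMC Charter does not settle the matter. As worded, it supersedes the IDMC section, 8.5.2, and not 6.1.

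**Conclusion.** Section 6.1 is wrong as written. This is a drafting conflict in the section that defines the automatic safety stop. It is not evidence of an intent to run Part 2 without one.

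Its size depends on which sequence is followed. Under the synopsis sequence, the 6.1.2 rules cover 0 of 1,600 planned doses, and no assumption is needed. Under 3.2.1 and 3.2.3, cover is at most roughly the first 8 to 9 weeks after the first Part 2 randomization, less review time.

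A reader might infer that most or all Part 2 doses fall outside the window on any sequence. The documents do not establish that. An overlap of 56 days with enrollment over 60 days would cover 70% of doses. That case is itself unrealistic: on the Day 8 reading it needs no review time at all, although IDMC review and FDA concurrence must both come first. Because review time and enrollment duration are not stated, no single share of doses should be quoted for the earlier-review sequence.

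The correction should be made before Part 2 dosing. It concerns safety, is specific, and costs little.

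**What to change.** Replace the single window in 6.1 with one for each part, for example:

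> The rules in 6.1.1 apply until the first Part 2 randomization or the close of the Part 1 Active Period, taking the later date. The rules in 6.1.2 apply from the first Part 2 randomization through the end of the study, and at minimum until 4 weeks after the last Part 2 dose.

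Then make the synopsis, 3.2.2 and 4.2.2 refer to these windows, so that every section gives the same period.

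Separate windows are better than extending all the rules to the whole study. With a whole-study window, rule 4 of 6.1.1 would let one severe COVID-19 case among the roughly 72 Part 1 participants, at any time up to Month 13, halt the 800-participant Part 2.

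The cost is two sentences in 6.1 and matching edits in three other places, with no new data, visits or roles. The small downside is that Part 1 follow-up events after the Part 1 window closes would go to IDMC oversight, which runs through the end of the study, and would not trigger an automatic halt.
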